Secondary outcome measures to examine how dentofacial, patient and practitioner characteristics influence a) treatment recommendations suggested by the orthodontists and b) acceptance of treatment recommendations by the patient include the following:

- Practitioner treatment recommendations include the practitioner's general strategies for openbite treatment (from practitioner characteristics form, e.g., whether and how often surgery is recommended), treatment recommendations (e.g. surgical option) presented to the patient, and patient's treatment goals (practitioner perspective);
- Patient acceptance of treatment recommendations includes the patient's self-report of the primary (ideal) treatment plan, whether or not the plan was accepted and why, and the patient's treatment goals;
- Dentofacial characteristics will be ascertained through examination and include: dental or skeletal nature of the openbite, millimetric measure of AOB, and amount of crowding;
- Patient characteristics include age, race, sex, insurance, and education; and
- Practitioner characteristics include the following: age, race, sex, years since received orthodontic training and orthodontic program.

Secondary outcome measures to examine how treatment modalities are associated with treatment success and patient satisfaction at the end of active treatment include the following:

- Treatment success is described above for the primary objective.
- Treatment modalities: Which teeth were extracted, if any; which if any of four treatment modalities were used (surgical component, fixed appliances, removable aligners, and/or TADs (mini-screws, mini-plates)).
- Patient satisfaction: The primary satisfaction measure will be overall satisfaction with treatment, (and secondarily, satisfaction with esthetics and function separately), ascertained by patient report at the end of active treatment.
- Other factors of interest for each include dentofacial characteristics (molar class, crowding, facial pattern, magnitude (millimeters) of overbite), practitioner characteristics (age, race, sex, years since received orthodontic training) and patient characteristics (age, race, sex, insurance, education, treatment

preference (whether patient agreed with primary recommendation), and patient treatment goal).

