Secondary outcome measures to examine how retainer regimens, as well as treatment modalities, dentofacial, patient and practitioner characteristics are associated with treatment stability and patient satisfaction one year after the end of active treatment include the following:

- Treatment stability is described above for the primary objective.
- Retainer regimens include: Type (Hawley, Essix, bonded), whether full-time or part-time (nights only) and compliance with these recommended regimens (ascertained through practitioner and, separately, patient self-report).
- Patient satisfaction: Overall satisfaction with retainers (and secondarily, satisfaction with esthetics and function separately), all of which will be ascertained by patient report at one year after end of active treatment.
- Other factors of interest for each include success of treatment at end of active treatment, and as described above, dentofacial characteristics (molar class, crowding, facial pattern, magnitude (millimeters) of overbite), treatment modalities (extraction, then surgical component, fixed appliances, removable aligners, TADs), practitioner characteristics (age, race, sex, years since received orthodontic training) and patient characteristics (age, race, sex, insurance, education, treatment preference (whether agreed with primary recommendation), and treatment goal).

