5 STUDY ENROLLMENT AND WITHDRAWAL

5.1 Inclusion Criteria

Practitioner:

In order to be eligible to participate in this study, a practitioner must meet all of the following criteria:

- Is enrolled in the National Dental PBRN as a practitioner who is licensed in the United States (US), and does treat patients in the US on a recurring basis.
- Is a “full” participation level member, or willing to change from “information only” or “limited” to “full”.
- Is trained and certified in Human Subjects Protection Training.
- Is willing to complete study-specific training.
- Has attended or viewed a National Dental PBRN orientation session or has attended at least one annual regional meeting of practitioners.
- Is an orthodontist or a dentist that routinely performs orthodontic treatment.
- Has a sufficiently large patient population such that the practitioner estimates he/she can recruit approximately 3 - 8 adult patients in active treatment for AOB, and expect to have treatment completed within 24 months of enrollment into the study.
- Routinely takes cephalometric x-rays before and after treatment.
- Has the ability to upload (via internet) de-identified cephalometric x-ray and digital intra-oral frontal photographs to a central repository.
- Affirms that the practice can devote sufficient time in patient scheduling to allow focused recording of all data required for the study.
- Does not anticipate retiring, selling the practice, or moving during the study.

Patient:

The patient population will come from the National Dental PBRN practices participating in this study.

In order to be eligible to participate in this study, a patient must meet all of the following criteria:

- Must be at least 18 years of age.
- Must have AOB that is defined as one or more incisors that do not have vertical overlap with teeth in the opposing arch. The remaining incisors may have minimal incisor overlap, but none of them can contact teeth in the opposing arch.
This will be determined by examining the patient’s initial cephalometric x-ray, intra-oral photographs, and/or initial plaster or digital casts.
- Must be in active treatment for AOB, and expect to have treatment completed within 24 months of enrollment into the study.

- Must have an initial cephalometric x-ray (taken prior to the beginning of treatment). A cephalometric x-ray created from a cone-beam CT scan is acceptable.

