7 STUDY PROCEDURES/EVALUATIONS

7.1 Study Procedures/Evaluations

Practitioner:

Prior to enrolling patients, the practitioner will complete a Practitioner Characteristics Form which will ascertain types and frequency of typical treatments and retention techniques used to treat adult patients presenting with an AOB.

Patient:

Enrollment. For each patient enrolled, the practitioner will complete an Enrollment Visit Form based upon clinical examination and review of records recording: 1) patients' reasons for seeking treatment; 2) pre-treatment diagnoses (dentofacial characteristics); 3) goals of treatment (practitioner perspective); and 4) treatment plan options, including adjunctive treatment, and treatment plan chosen.

De-identified initial cephalometric x-ray and intra-oral frontal photographs taken prior to treatment initiation will be uploaded for measures of dentofacial characteristics, such as overbite, mandibular plane angle, and incisor angulation (as described above in outcome measures).

At enrollment, after consent, the patient will complete a Patient Enrollment Visit form, which elicits 1) age (from year of birth and date), race/ethnicity, sex, insurance, education; 2) reasons for seeking treatment; 3) treatment recommended as ideal (patient perspective); 4) whether or not accepted ideal recommendation, and if not, why not; and 5) previous orthodontic treatment, if any.

End of active treatment. The practitioner will complete an End of Active Treatment Form based upon clinical examination and review of treatment records recording: 1) any changes in originally accepted treatment plan; 2) treatment result and expected stability outcome; 3) any residual oral habits; 4) patient compliance and adjunctive treatments; 5) current molar relationship; and 6) retention techniques recommended.

De-identified end of active treatment cephalometric x-ray and intra-oral frontal photograph taken in maximum intercuspation will be uploaded for measures of overbite. Practitioner will also obtain an additional intra-oral frontal photograph taken with the incisors slightly apart and upload the de-identified photo for measures of overbite. The practitioner will also measure the height of the right maxillary central incisor using the provided metal ruler.

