11.4.2 Proposed Secondary Analyses

Analysis plan for Secondary Objectives:

Secondary objective #1a will examine how dentofacial, as well as patient and practitioner characteristics influence treatment recommendations suggested by the orthodontists. The association of each of the dentofacial, patient and practitioner characteristics specified below with different treatment recommendations will be ascertained using a chi-square test for categorical variables and either t-test or Wilcoxon rank-sum test (nonparametric equivalent). Dentofacial characteristics: profile, molar classification, maxillary crowding, mandibular crowding, posterior cross-bite, facial pattern. Patient characteristics: age, sex, race/ethnicity, insurance, education, treatment goals. Practitioner characteristics: age, sex, race/ethnicity, year received orthodontic training. For each domain of the three domains, namely, dentofacial, patient and practitioner characteristics, characteristics with $p < 0.2$ will be entered in the model, retained if $p < 0.1$. Final Generalized Estimating Equations (GEE) regression model (adjust for clustering within practice) will start with those $p < 0.1$ for each domain, and retained if $p < 0.05$ for final analysis ascertaining how dentofacial, as well as patient and practitioner characteristics influence treatment recommendations (extraction, then surgical component, fixed appliances, removable aligners, TADs).

Secondary objective #1b will examine how dentofacial, as well as patient, practitioner, characteristics influence whether or not treatment recommendations suggested by the orthodontists are accepted by the patients. Method described above will be repeated for acceptance of recommendations. Separate analyses, i.e., stratum specific, will be performed for recommendations involving extraction and those not. Of interest (though not a primary objective or specific hypothesis to be tested) within this secondary objective is exploring what factors influence whether or not patients accept treatment recommendations involving an extraction or surgical component.

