Secondary objective #2a will identify how treatment modalities, as well as dentofacial, patient and practitioner characteristics, are associated with treatment success. Success is defined above, first as positive overbite, then as amount of millimetric improvement, even if AOB is not completely closed as described in analysis for primary objective #1 above. Separate analyses, i.e., stratum specific, will be performed for treatment involving extraction and those not. The association of treatment modalities used will be assessed with whether or not treatment was successful using chi-square. The dentofacial, patient and practitioner characteristics described above, and the process to ascertain their influence on treatment recommendations, will be used to determine their association with treatment success. The process, being domain specific, will model criteria entry if $p < 0.2$; retain at $p < 0.1$. Final model, all domains combined, entry if $p < 0.1$; retained if $p < 0.05$. For this secondary objective (2a), treatment modalities will be included, first as a domain in the same manner that dentofacial, patient, and practitioner characteristics are. Then, stratum specific analyses will be performed separately according to whether or not there was an extraction.

Secondary objective #2b will identify how treatment modalities, as well as dentofacial, patient and practitioner characteristics, are associated with patient satisfaction. The above process will be repeated except the “outcome” will be patient satisfaction instead of treatment success. Separate models will be developed for overall or general

satisfaction, and for satisfaction with esthetics and with function. For this objective, whether or not treatment was successful, will be analyzed as an independent variable. A high association is expected, namely, more patients will be satisfied when treatment is successful than when not; however, it will not be a 100% (perfect) association. Some patients who are treated successfully will not be satisfied, and in contrast, some patients who are not treated successfully will be satisfied. Quantification of these proportions is of interest, as well as identifying characteristics (treatment modalities, dentofacial, patient and practitioner) that are associated with satisfaction (or dissatisfaction).

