Secondary objective #3a will examine how retainer regimens, as well as treatment modalities, dentofacial, patient and practitioner characteristics are associated with treatment stability. Stability is defined above, namely, at one year after end of active treatment there is positive overbite. First, the association of retainer regimens, namely, type of retainer (Hawley, Essix, bonded) and frequency of use prescribed (full or part-time) with treatment stability will be assessed with chi-square test. The treatment modalities (extraction, then surgery, fixed appliances, removable aligners, or TADs), dentofacial, patient and practitioner characteristics described above, will be used to ascertain their association with treatment stability. The process, being domain specific, will model criteria entry if $p < 0.2$; retain at $p < 0.1$. Final model, all domains combined, entry if $p < 0.1$; retained if $p < 0.05$. For this secondary objective (3a), retainer regimens will be included, first as a domain in the same manner that treatment modalities, dentofacial, patient, and practitioner characteristics are. Then, stratum specific analyses will be performed separately according to whether or not treatment included extraction and whether or not treatment was successful (AOB closed at end of active treatment).

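### The fixed practitioner covariate list omits orthodontist versus dentist, so the modality and retainer associations in objectives 2a and 3a may be partly confounded by provider type (minor)

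*Protocol*

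**What the plan says.** Section 11.4.2 lists the candidate covariates under objective 1a. For the practitioner domain it gives: "Practitioner characteristics: age, sex, race/ethnicity, year received orthodontic training". The list is then carried forward. For treatment success (2a): "The dentofacial, patient and practitioner characteristics described above, and the process to ascertain their influence on treatment recommendations, will be used". For stability (3a): "dentofacial, patient and practitioner characteristics described above, will be used to ascertain their association with treatment stability". Objectives 1b, 2b and 3b repeat the same procedure. Variables enter and stay by p-value, within each domain first and then across domains. The final model is a GEE that allows for clustering within practice.

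Section 3.2 is slightly wider for objective 1: "Practitioner characteristics include the following: age, race, sex, years since received orthodontic training and orthodontic program". For objectives 2 and 3 it returns to the short list, without the program.

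The practitioner inclusion criteria in section 5.1 admit two kinds of provider: "Is an orthodontist or a dentist that routinely performs orthodontic treatment". Section 6.1 has these criteria verified at practitioner screening.

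Section 7.1 says that the Practitioner Characteristics Form, completed before any patient is enrolled, records "types and frequency of typical treatments and retention techniques used to treat adult patients presenting with an AOB". No success or stability model uses this information.

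**The concern.** Modality and retainer are chosen by practitioner and patient; nothing is assigned. Who treats is therefore an obvious alternative explanation for any association between modality and closure, or between retainer and stability. Provider type is a natural candidate: it may be related to the techniques offered and to the results, and the protocol deliberately admits both types. A list restricted to demographics and training year cannot adjust for it.

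The GEE does not fill the gap. Allowing for clustering gives valid standard errors, but it does not remove confounding between practitioners. The p-value screen can also discard the practitioner variables that are listed.

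At stake is the reading of the 2a and 3a contrasts, which the background section presents as evidence on which methods are most effective and stable.

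**Working it through.** **1. Comparing the lists**

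| Item | 3.2, objective 1 | 3.2, objectives 2 and 3 | 11.4.2, objectives 1a to 3b |
|---|---|---|---|
| Age, sex, race | yes | yes | yes (race/ethnicity) |
| Time of orthodontic training | yes | yes | yes |
| Orthodontic program | yes | no | no |
| Orthodontist or dentist | no | no | no |
| Usual technique | under recommendations, not as a covariate | no | no |

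Provider type is absent throughout. The program is in one list for objective 1 and missing from the other.

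**2. The plan's own yardstick**

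Section 11.4.1 aims to detect a 20-point difference with 110 patients per group (80% power, 5% level, ICC 5%). Two-sided testing is assumed here, with pooled variance and no continuity correction. For 40% versus 60% this gives 97 per group before clustering. The design effect is 1 + (m − 1) × 0.05.
- m = 3: 97 × 1.10 = 106.7
- m = 4: 97 × 1.15 = 111.5

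The 110 is reproduced to within 3%.

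**3. Possible size of the bias (assumed inputs)**

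The protocol gives no dentist share, no technique use by provider type and no outcome gap. Suppose that modality has no effect. Let q be the share of patients treated by dentists, a and b the aligner use among dentists' and orthodontists' patients, and D the gap in success. Then

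s = qa/[qa + (1 − q)b] − q(1 − a)/[q(1 − a) + (1 − q)(1 − b)], and the spurious difference = s × D.

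| q | a vs b | D (points) | Dentist share, aligner | Dentist share, other | s | Spurious difference (points) |
|---|---|---|---|---|---|---|
| 1% | 60% vs 20% | 10 | 0.006/0.204 = 0.029 | 0.004/0.796 = 0.005 | 0.024 | 0.2 |
| 5% | 60% vs 20% | 10 | 0.030/0.220 = 0.136 | 0.020/0.780 = 0.026 | 0.111 | 1.1 |
| 15% | 70% vs 20% | 15 | 0.105/0.275 = 0.382 | 0.045/0.725 = 0.062 | 0.320 | 4.8 |
| 20% | 70% vs 20% | 20 | 0.140/0.300 = 0.467 | 0.060/0.700 = 0.086 | 0.381 | 7.6 |

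A wider grid sets D and s directly, with 110 per group, design effect 1.15 and average success 70%. The last figure on each line is the chance of a significant result in the direction of the bias, nominally 2.5%.
- D = 5, s = 0.1: 0.5 points, 3.0%
- D = 10, s = 0.3: 3 points, 6.6%
- D = 20, s = 0.5: 10 points, 32.5%

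The range therefore runs from negligible to half of the 20-point target.

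**4. Cost of forcing usual technique into the main model (assumed inputs)**

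Suppose that 30% of patients have a practitioner who often uses TADs, with TADs placed in 60% of those patients and 10% of the rest.
- Overall TAD use: 0.3 × 0.6 + 0.7 × 0.1 = 0.25
- Correlation of habit with TAD use: 0.5 × √(0.3 × 0.7)/√(0.25 × 0.75) = 0.53
- Variance inflation: 1/(1 − 0.53²) ≈ 1.39
- Effective group size: 110/1.39 ≈ 79

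**The case against.** The strongest reply is that dentists may be very few. Section 11.2 counts about 210 orthodontists, section 11.4.2 speaks of recommendations made by orthodontists, and section 5.3.1 recruits through the orthodontists' association. At 1% dentists the bias is about 0.2 points. The objectives are also secondary and worded as associations, and an SAP, not at hand here, could extend the list. All of this limits the severity. It does not remove the gap: the protocol admits both types, and the list it fixes cannot separate them.

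A reader might infer more than the documents support:

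- **That provider type and usual technique are both recorded.** This is explicit only for technique. Provider type must be known to apply section 5.1, but no section names it as a data field, and the content of the network enrollment questionnaire is not given.
- **That the comparisons do compare who treats rather than what is done.** That needs a provider mix and an outcome gap, and the protocol states neither.
- **That dentists' patients will drop out of the models for want of a training year.** That requires dentists without such a year, a complete-case analysis, and training year surviving the screen. None is stated, and the handling of missing covariates is properly left to an SAP.
- **That section 3.2 makes practitioner habit an outcome.** It does list "general strategies for openbite treatment (from practitioner characteristics form, e.g., whether and how often surgery is recommended") under treatment recommendations, but the same block mixes outcomes with predictors, and section 11.4.2 models only recommendations made for individual patients. This is loose labelling.
- **That usual technique should be forced into the main models.** Habit strongly predicts modality and may act on outcome mainly through it. Conditioning on such a near-instrument need not reduce bias, can amplify residual confounding, and costs precision.

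**Conclusion.** The point holds as a minor one. The practitioner list in section 11.4.2 is fixed, is reused through objective 3b, omits provider type although both types are eligible, and disagrees with section 3.2 on orthodontic program for objective 1. The modality and retainer associations in 2a and 3a may therefore be partly confounded by provider type, and the GEE does not correct that.

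The size cannot be derived from the protocol. The figures from 0.2 to 10 points rest wholly on assumed shares and gaps, and the low end applies if dentists are very few. The primary estimates of success and stability are single proportions and are not touched.

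**What to change.** - Carry provider type (orthodontist or dentist) from eligibility screening into the analysis data and add it to the practitioner domain in sections 3.2 and 11.4.2.
- If dentists are more than a handful, keep it in the 2a and 3a models whatever the p-value screen says. If they are very few, report the number and say so.
- Define training year so that dentists have a value or a category.
- Reconcile orthodontic program between sections 3.2 and 11.4.2: include it in both or in neither.
- Use the stated usual technique, already collected on the practitioner form, only in a sensitivity model; or split modality into within- and between-practitioner parts.

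The cost is a few lines of wording, one extra model term and one sensitivity analysis, with wider intervals in that sensitivity analysis. Usual technique needs no new collection; provider type needs only to be carried over from screening.

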11.4 Secondary Analyses

11.4.1 Sample Size Considerations

For secondary objectives, we wish to detect differences of 20% in success and stabilization rates between subgroups, e.g., differences between patients for whom extraction was recommended and those for whom it was not. In general, we will need 110 patients for each group that is being compared (assuming 80% power, 5% significance level, and an ICC of 5%). For example, for the assessment of success between extraction and non-extraction cases, we need 110 patients treated with each technique. For the comparison of the four treatment modalities, we need 110 patients treated with each of the 4 techniques, or 440 patients total. If we recruit 840 patients at baseline, we should have adequate power for most secondary objectives, even allowing for attrition.

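### Objective 2a relates success to the modalities finally used and has no analysis by the originally accepted plan, so response-driven plan changes could distort the comparison of modalities

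*Protocol*

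**What the plan says.** - **Exposure.** Protocol 3.2 defines treatment modality as "which if any of four treatment modalities were used (surgical component, fixed appliances, removable aligners, and/or TADs (mini-screws, mini-plates". It is a record of treatment received, and the and/or allows one patient several modalities.
- **Analysis.** For objective 2a, 11.4.2 states: "The association of treatment modalities used will be assessed with whether or not treatment was successful using chi-square". Modality then enters the model as a domain, alongside dentofacial, patient and practitioner characteristics.
- **Plan and changes.** Under 7.1 the practitioner records at enrolment "treatment plan options, including adjunctive treatment, and treatment plan chosen", and at the end of active treatment "any changes in originally accepted treatment plan". Neither item appears as an exposure in the 2a analysis.
- **Timing.** Patients join while already under treatment (5.1): "Must be in active treatment for AOB, and expect to have treatment completed within 24 months of enrollment into the study". Some plan changes can therefore precede enrolment.
- **Sizing.** In 11.4.1, "we wish to detect differences of 20% in success and stabilization rates between subgroups", and for the modality comparison "we need 110 patients treated with each of the 4 techniques, or 440 patients total". The same section illustrates its subgroups first by whether extraction was recommended and then by the technique patients were treated with.

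**The concern.** A patient may start on one approach, make poor progress and have a second modality added. By appliance removal that patient is classified partly or wholly by the second modality. If the change was made because the bite was not closing, group membership depends on an early reading of the outcome being compared. The first modality may then be relieved of its poor responders while the added one takes them in. The model in 11.4.2 does not remove this: the characteristics listed there contain no measure of progress during treatment.

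The objective is worded as association, but section 2.1 gives a comparative motive. It says that it is unknown which treatment is better or more stable, and that temporary anchorage devices would be preferable to surgery if results were similar. A difference between modalities that partly reflects who was escalated would be read as bearing on that question.

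The group count adds a second difficulty. Four groups of 110 make 440 different patients only if each patient belongs to one group, which the definition in 3.2 does not ensure.

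**Working it through.** **1. The plan's own figure.** Inputs from 11.4.1: 20-point difference, 80% power, 5% significance (two-sided assumed), ICC 0.05. Cluster size from 11.2: 3 patients per practitioner in the sizing, about 4 recruited. Base rates are not given in 11.4.1 and are assumed here. Formula: two-proportion sample size with pooled variance, no continuity correction, times the design effect 1 + (m - 1) x 0.05.

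- 40% vs 60%: 97 per group; x 1.10 = 107 (m = 3); x 1.15 = 112 (m = 4).
- 50% vs 70%: 93 per group; x 1.15 = 107 (m = 4).

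The stated 110 per group is reproduced to within 3% and is not in dispute.

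**2. What classification by use can do when there is no true difference.** All inputs in this step are assumptions. Two starting strategies, A and B, have 110 patients each and equal success by starting strategy. In A, a share *f* is not closing; a share *e* of those is escalated to B; escalated patients succeed with probability *r*. Each patient is put in one group by the most invasive modality used.

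- Success by starting strategy, both arms: s = (1 - f) + f·e·r
- A as used: (1 - f) / (1 - f·e)
- B as used: (s + f·e·r) / (1 + f·e)

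Worked case, f = 0.30, e = 0.50, r = 0.30: f·e = 0.15; s = 0.70 + 0.045 = 0.745 in both. A as used = 0.70/0.85 = 0.824. B as used = 0.790/1.15 = 0.687. The apparent difference is +13.7 points; the true one is 0.

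Apparent A minus B, in percentage points:

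| f | e | r = 30% | r = 50% | r = 70% |
|---|---|---|---|---|
| 30% | 10% | +2.5 | +1.3 | +0.1 |
| 30% | 25% | +6.4 | +3.6 | +0.8 |
| 30% | 50% | +13.7 | +8.4 | +3.2 |
| 50% | 10% | +2.2 | +0.3 | -1.7 |
| 50% | 25% | +6.0 | +1.6 | -2.9 |
| 50% | 50% | +14.7 | +6.7 | -1.3 |

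The range is -2.9 to +14.7; 7 of the 18 cells lie within 2 points of zero. With a design effect of 1.10, the probability of a significant result in the one direction (0.025 without distortion) rises to about 0.60 in the worked case, the highest of the 18.

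**3. The same scenarios with overlapping groups.** If an escalated patient counts under both modalities, A is s and B is as above, so the difference is f·e·(s - r)/(1 + f·e). In the worked case this is 0.15 x 0.445/1.15 = +5.8 points. At f = 0.50, e = 0.25, r = 0.70 it is 0.125 x (0.5875 - 0.70)/1.125 = -1.3 points. These are the extremes of the 18 cells. The distortion is smaller, but the groups now share patients, so an ordinary two-group chi-square does not apply. If each modality is instead tested as used versus not used, the contrast for the added modality in this two-strategy set-up is again the one in the table.

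**The case against.** **Association with treatment received is a legitimate question.** Objectives 2 and 3 are worded as associations in an observational cohort, and describing success by modality received answers that. This stands, and it is why the analysis by modality used should stay.

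**No source shows that changes are response-driven.** Section 7.1 records changes to the plan; no section gives their frequency, direction or reason. This also stands. The scenarios show what could happen, not what will.

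**Escalated patients need not leave their starting group.** Under the and/or definition in 3.2 they can count under both modalities. A reader might infer that the ranking of modalities will reverse. Suppose 110 patients start on aligners and 66 close without a change; of the other 44, 22 are switched and 11 of those close. The comparator has 110 patients at 75%. With exclusive groups, aligners read 66/88 = 75% against (82.5 + 11)/132 = 71%, whereas by plan they stand at 77/110 = 70% against 75%. That reversal rests on assumptions the documents do not supply. Counting switched patients under both modalities gives 77/110 = 70% against 93.5/132 = 71%, with no reversal. With 25% of the 44 switched, exclusive groups give 66/99 = 66.7% against 88/121 = 72.7%, again no reversal.

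**The shift is easily overstated.** Setting the 60% who close without a change against the 75% as used suggests 15 points, but it mixes two outcomes, because success in the protocol is closure at the end of treatment with or without a plan change. Like for like, the contrast moves from -5 to about +4, roughly 9 points.

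**The problem does not extend to stability.** Modality received is complete at appliance removal, before the one-year outcomes begin, so escalation for failure to close cannot be a response to later relapse. Objective 3a also stratifies by whether treatment succeeded. Modality received is a natural exposure for 3a and 3b.

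**Coding of combinations can be left to the SAP.** In general it can. But the protocol itself fixes the 2a exposure as modality used, and it also fixes a four-group count that its own definition does not support.

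**Conclusion.** The point holds in a conditional form. For 2a the protocol fixes as exposure something known only when the outcome is known. It foresees and records plan changes, and it specifies no analysis by the plan with which the patient started. If escalation follows poor progress, the comparison of modalities on success can be distorted, and the planned analysis could not separate that from a modality effect.

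The size and sign are unknown. With two equally successful starting strategies and exclusive groups, the assumed scenarios give about -3 to +15 points, near zero in several, against a 20-point target. The documents do not support saying that the comparison is biased, that the ranking will reverse, or that 3a and 3b share the problem.

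The mismatch between four separate groups in 11.4.1 and overlapping modalities in 3.2 stands independently of how often plans change. The primary objectives and the 110 per group are unaffected.

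**What to change.** 1. In 11.4.2, for objective 2a, add a pre-specified analysis of success by the originally accepted plan from the practitioner's Enrollment Visit Form, reported beside the analysis by modality used. Repeat it for 2b as a sensitivity analysis.
2. Define the plan groups as mutually exclusive under a stated rule. One option is an ordered classification: surgical component; anchorage devices without surgery; aligners without either; fixed appliances only.
3. State that the variable is the originally accepted plan, not the plan current at enrolment, since patients join during treatment.
4. Report a cross-table of planned by used modality, and closure with and without a change of plan.
5. Keep modality received as the main exposure for 3a and 3b.
6. Reconcile the four-group count in 11.4.1 with the and/or definition in 3.2, and use one term where that section now moves between recommended and treated with.

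The cost is analysis wording, one derived variable and a little more analysis work. The plan chosen and its changes are already collected. Some planned-modality groups may be smaller than 110.
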